**Table 7-2 Protocol Risk Assessment and Mitigation Strategies**

Potential Risk of Clinical Significance	Mitigation Strategy	
	Impact on Eligibility	Monitoring and Withdrawal Criteria
Bone Mineral Density Reversible loss of bone mineral density is a risk of the hypoestrogenic state induced by relugolix. This risk is mitigated by the co-administration of low-dose estradiol and norethindrone acetate hormonal add-back therapy.	Exclusion criteria for a history of osteoporosis, metabolic bone disease, and prior medical therapy for low bone mineral density was included in the parent studies.	Bone mineral density will be monitored at the Week 24/Baseline, Week 36, Week 52, and Week 104/Early Termination visits with specified discontinuation and follow-up criteria and all fractures will be reported as adverse events.
Drug Interactions	Exclusion of co-administration P-glycoprotein inhibitors/inducers.	Collection of adverse events.

Potential Risk of Clinical Significance	Mitigation Strategy	
	Impact on Eligibility	Monitoring and Withdrawal Criteria

QTc Prolongation
 
Negative Thorough QT/QTc clinical study.
	
Empiric exclusion of baseline QTcF > 470 msec in the parent studies.
	
12-lead ECG at the Week 24/Baseline and Week 52 visits, and as clinically applicable; withdrawal for QTcF > 500 msec.

Hepatic Enzymes
 
Isolated increases in hepatic transaminases have been observed in prior clinical studies. There have been no reported cases consistent with drug-induced liver injury including an increase in bilirubin. Abnormal liver test results are considered adverse events of clinical interest in this study.
	
Exclusion criteria for AST and ALT > 2 × the ULN; total bilirubin values > 1.5 × ULN.
	
Abnormal liver test results (AST or ALT > 3 × ULN) that develop during the Open-Label Treatment Period will be reported within 24 hours of study personnel awareness.


Phospholipidosis
 
Data from nonclinical studies in rats and monkeys showed histopathological changes consistent with PLD. PLD by itself is not adverse. No clinical evidence of relugolix-related PLD-associated toxicity has been observed nor was there a clinically meaningful increase in a biomarker of PLD assessed in phase 2 clinical studies.
	
Patients with significant underlying medical conditions are excluded.
	
Routine safety monitoring including laboratory assessments, ECGs, and assessment of adverse events, including any ophthalmologic adverse events, will be monitored during this study.

Metabolic Changes
 
Metabolic changes (insulin resistance, dyslipidemia, and increased weight) with increased risk of diabetes are a potential risk of the hypoestrogenic state induced by relugolix.
	
Exclusion criteria for current medical history of cardiovascular disease in the parent studies.
	
Fasting lipids and glucose will be monitored during the study.

Reproductive Toxicity
	
Premenopausal compliance with specified acceptable non-hormonal contraception; exclusion of pregnant and lactating women.
	
Pregnancy testing at each study visit; immediate withdrawal for pregnancy.

Potential Risk of Clinical Significance	Mitigation Strategy	
	Impact on Eligibility	Monitoring and Withdrawal Criteria

Risk of Estradiol (1.0 mg)/Norethindrone Acetate (0.5 mg)
 
Low-dose estradiol and norethindrone acetate are approved for the prevention of postmenopausal osteoporosis and the treatment of moderate to severe vasomotor symptoms. It is contraindicated for women with a history of breast cancer or estrogen-dependent neoplasia, history of (or active) deep vein thrombosis, pulmonary embolism, thromboembolic disease (myocardial infarction or stroke within the past year), liver dysfunction, prior hypersensitivity, and pregnancy.
	
Women with breast cancer or other estrogen-dependent malignancies, a history of deep vein thrombosis, pulmonary embolism, thromboembolic disease, liver dysfunction, prior hypersensitivity, migraine with aura, porphyria, and pregnancy excluded from the parent studies. Physical examination, clinical chemistries, and 12-lead ECG will be performed at the Week 24/Baseline visit.
	
Clinical chemistries assessing liver tests, fasting glucose and lipids, and urine pregnancy tests will be performed throughout the study. Adverse events will be recorded at each study visit;
 
A mammogram will be performed at Week 52 or at the Week 104/Early Termination visit for women who are or become <math>\geq 40</math> years old during the study, with specified discontinuation criteria. Adverse events will be recorded.

ALT = alanine aminotransferase; AST = aspartate aminotransferase; ECG = electrocardiogram; QTc = corrected QT interval; QTcF = QT interval by the Fridericia correction; PLD = phospholipidosis; ULN = upper limit of normal.

---

## **8. DATA QUALITY ASSURANCE**

### **8.1. Clinical Procedures**

Sponsor personnel or designee(s) will visit the study site, if necessary, prior to initiation of the study to review information about the study drug, protocol requirements, eCRFs, monitoring requirements, reporting of serious adverse events, and to ensure a full understanding of the Investigator Site File with the site personnel.

### **8.2. Monitoring**

This study will be monitored by the sponsor (or designee) in accordance with current Good Clinical Practice (GCP) regulations. By signing this protocol, the investigator grants permission to Myovant Sciences GmbH (or designee) and appropriate regulatory authorities to conduct on-site monitoring of all appropriate study documentation. In order to assure the accuracy of data collected in the eCRF, it is mandatory that representatives of the sponsor (or designee) have access to original source documents (eg, patient records, patient charts, and laboratory reports). During the review of these documents, the anonymity of the patient will be respected with strict adherence to professional standards of confidentiality. A study monitor will contact and visit the site regularly and will be allowed, on request at a mutually acceptable time, to inspect the various records of the study. It will be the study monitor's responsibility to inspect the eCRF at regular intervals throughout the study, to verify the adherence to the protocol and the completeness, correctness and accuracy of all eCRF entries, and to meet with the investigator to discuss study progress and compliance with the protocol and GCP. The study monitor should have access to laboratory test results and any other source records and data needed to verify the entries on the eCRF. The investigator agrees to cooperate with the study monitor to ensure that any problems detected in the course of these monitoring visits are resolved. For this study, patient data will be entered into a sponsor-approved electronic database and combined with data provided from other sources in validated datasets then transmitted electronically to the sponsor (or designee).

Management of clinical data will be performed in accordance with applicable sponsor-approved standards and data cleaning procedures to ensure the integrity of the data (eg, removing errors and inconsistencies in the data).

Adverse events and concomitant medications terms will be coded using the Medical Dictionary for Regulatory Activities (MedDRA) and the World Health Organization Drug Dictionary Enhanced (WHO-DDE), respectively.

The investigator will retain original source documents and the sponsor will receive eCRF-required data as electronic datasets. Patient initials will not be collected or transmitted to the sponsor.

---

## **9. STATISTICAL CONSIDERATIONS AND DATA ANALYSES**

A statistical analysis plan (SAP) will describe the detailed statistical methods and analyses for this study.

All efficacy and safety measures over the course of both the parent and extension studies will be presented by the parent study treatment group using descriptive statistics. No formal treatment comparisons will be performed for this extension study. Continuous data will be summarized by means, standard deviations, medians, maximum, minimum, and number of patients. Categorical data will be summarized by counts and percentages.

There will be two analyses: one at Week 52 and one at Week 104. A clinical study report will be generated from each analysis.

The study may be closed pending selected contingent safety procedures conducted after the last patient's Week 104/Early Termination or Follow-Up visit. After the study is closed, any pending required follow-up testing of bone mineral density and endometrial biopsies or for menstruation recovery beyond the Follow-Up visit will be captured and reported.

### **9.1. Randomization Methods**

This is a single-arm, open-label extension study; patients are not randomized. All patients who have entered the extension study will be treated with open-label relugolix and low-dose hormonal add-back therapy for 80 weeks.

### **9.2. Analysis Populations**

Efficacy data analyses will be performed on the Extension Study Population, defined as all patients who enrolled into MVT-601-3103 and who have received any amount of randomized open-label study drug in MVT-601-3103.

Safety data analyses will be performed on the Safety Population, defined as all enrolled patients who have received any amount of MVT-601-3103 study drug.

The analysis methods for safety and efficacy endpoints are the same as those used for the parent studies, unless otherwise specified in the SAP.

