### Safety

Safety assessments will include treatment-emergent adverse events, vital signs and weight, physical examinations, clinical laboratory tests, 12-lead ECG, bone mineral density with DXA scan, mammograms (for patients required to have this procedure, see Section 6.5.2.9), and endometrial biopsy. Safety data analyses will use data from all patients from the parent studies who receive any amount of study drug (ie, from parent study Baseline to Week 52 or Week 104).

Drug exposure will be summarized by descriptive statistics. Severity of all treatment-emergent adverse events will be evaluated by the investigator based on the National Cancer Institute Common Terminology Criteria for Adverse Events (CTCAE) and will be coded to preferred term, high level term, and system organ class using the Medical Dictionary for Regulatory Activities (MedDRA). The number and percentage of patients with adverse events will be presented by MedDRA system organ class and preferred term, relationship to study drug, and severity. Laboratory values will be classified by toxicity grade based on the National Cancer Institute CTCAE. Laboratory shift tables of the parent study Baseline results to each of the subsequent visits will be produced.

Bone mineral density will be evaluated in all patients at the lumbar spine (L1-L4), femoral neck, and total hip at the Week 24/Baseline, Week 36, Week 52, and Week 104/Early Termination visits. The absolute change and percent change from parent study Baseline and Z-scores will be summarized by visit and parent study treatment group.

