#### **4.3.1. Inclusion/Exclusion Criteria**

Inclusion Criteria (all inclusion criteria must have been met prior to randomization):

1. Completed 24 weeks of study drug treatment and study participation in either MVT-601-3101 or MVT-601-3102;
2. Has voluntarily signed and dated the informed consent form prior to initiation of any study-specific procedures for MVT-601-3103;

Note: Procedures conducted as part of the parent study that also serve as baseline procedures for this study will be done under the informed consent for the parent study.

3. Is not expected to undergo gynecological surgery or other surgical procedures for treatment of endometriosis (including ablation, shaving, or excision) during the study, including during the Follow-Up Period, and the patient does not desire such treatment during this time frame;
4. Has a negative urine pregnancy test at the Week 24/Baseline visit;
5. Has agreed to continue to use only study-specified analgesic medications during the study and is not known to be intolerant to these;
6. Agrees to continue to use acceptable non-hormonal contraceptive methods as described in Section 4.6 consistently during the Open-Label Treatment Period and for at least 30 days after the last dose of study drug. However, the patient is not required to use the specified non-hormonal contraceptive methods if she:
  - a. Has a sexual partner(s) who was vasectomized at least 6 months prior to the Week 24/Baseline visit;
  - b. Had a bilateral tubal occlusion (including ligation and blockage methods such as Essure™), at least 6 months prior to the Week 24/Baseline visit (patients with Essure must have prior confirmation of tubal occlusion by hysterosalpingogram) and there must be no evidence of post-Essure syndrome;
  - c. Has a non-hormonal intrauterine device (eg, Paragard®) placed in the uterus;
  - d. Is not sexually active with men; periodic sexual relationship(s) with men requires the use of non-hormonal contraception as noted above;
  - e. Practices total abstinence from sexual intercourse, as her preferred lifestyle; periodic abstinence is not acceptable.

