## 9.5. Safety Analyses

Safety assessments will include treatment-emergent adverse events, vital signs and weight, physical examinations, clinical laboratory tests, 12-lead ECG, bone mineral density with DXA, mammograms (for patients required to have this procedure, see Section 6.5.2.9), and endometrial biopsy. Safety summaries by treatment group will be performed using treatment groups defined based on the actual randomized treatment received in the parent study.

The treatment-emergent period will be defined as the period of time from the first dose date and time of randomized study drug in the parent study through 30 days after the last dose of study drug, or the date of initiation of another investigational agent or hormonal therapy affecting the hypothalamic-pituitary-gonadal axis or surgical intervention for endometriosis, whichever occurs first. Safety will be assessed through summaries of adverse events, the frequency of treatment discontinuations due to adverse events, laboratory evaluations, and bone densitometry results.

The severity of all adverse events is to be evaluated by the investigator based on the National Cancer Institute CTCAE. All adverse events will be coded to preferred term, high level term, and system organ class using MedDRA 20.0 or higher. The incidence of adverse events will be presented by MedDRA system organ class and preferred term, relationship to study drug treatment, and severity. A patient reporting the same adverse event more than once is counted

once, and at the maximum severity or strongest relationship to study drug treatment when calculating incidence.

Laboratory data consist of chemistry, hematology, and hormonal tests. Only data collected by the central laboratory will be used to do the analyses. The National Cancer Institute CTCAE will be used to categorize toxicity grade for the laboratory parameters. Shift tables will be provided for each gradable parameter to summarize baseline toxicity grade versus post-baseline toxicity grade. For laboratory parameters that are not gradable by the CTCAE, a shift table based upon the normal range (low, normal, and high) will be provided for each parameter to summarize the parent study Baseline versus post-baseline results. All data will be listed and summarized by visit. The change from parent study Baseline to each post-baseline study visit will be presented by parent study treatment group for each laboratory test.

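### The protocol gives two incompatible safety populations, and the Section 9.2 population on a clock starting at the first parent dose cannot show adverse-event discontinuations in Weeks 0-24

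*Protocol*

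**What the plan says.** All the text below is from the current version of the protocol (Amendment 3.1).

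- **Section 9.2, Analysis Populations:** "Safety data analyses will be performed on the Safety Population, defined as all enrolled patients who have received any amount of MVT-601-3103 study drug".
- **Synopsis, Statistical Methods, Safety:** "Safety data analyses will use data from all patients from the parent studies who receive any amount of study drug", with the window given as "from parent study Baseline to Week 52 or Week 104".
- **Section 9.5, Safety Analyses:** the treatment-emergent period is "the period of time from the first dose date and time of randomized study drug in the parent study". It closes 30 days past the final dose, or sooner if certain other therapies or endometriosis surgery come first. One of the listed safety summaries is "the frequency of treatment discontinuations due to adverse events".
- **Section 9, opening text:** efficacy and safety are presented across the parent and extension studies by parent treatment group.
- **Section 4.3.1:** inclusion criterion 1 reads "Completed 24 weeks of study drug treatment and study participation in either MVT-601-3101 or MVT-601-3102". Exclusion criterion 13 bars anyone who met a parent-study withdrawal criterion.
- **Section 9.3:** about 800 of the 1200 patients to be randomized in the parent studies (67%) are expected to enter.

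**The concern.** There are two linked problems.

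First, the synopsis and Section 9.2 name different sets of patients. Section 9.2 leaves analysis methods to the SAP but fixes the population itself, so a SAP cannot follow both passages.

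Second, the Section 9.2 population does not fit the clock in Section 9.5. The treatment-emergent period opens about 24 weeks before a patient can join the population, and she can join only by having stayed on treatment for those weeks. Any patient who stopped permanently for an adverse event in the parent study is absent from both numerator and denominator.

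Safety is a stated objective, and Section 9.8 says the Week 52 report is to support a submission of one-year data. A pooled adverse-event discontinuation percentage over parent plus extension could be taken as the risk from starting treatment, which in this population it is not.

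**Working it through.** **1. The plan's own figure.** Section 9.3 gives 800 and 1200. 800/1200 = 66.7%, which rounds to the stated 67%.

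**2. Size of the disagreement.** 1200 - 800 = 400 patients, or 400/1200 = 33%, are in the synopsis set but not the Section 9.2 set. Both inputs are planning figures. The 1200 counts randomized patients, so it is an upper bound on those treated.

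**3. Discontinuations in Weeks 0-24.** In the Section 9.2 population the number of permanent adverse-event discontinuations in this interval is zero by construction, because of inclusion criterion 1 and exclusion criterion 13.

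**4. Shortfall in discontinuation risk.** Let d be the risk of stopping for an adverse event in Weeks 0-24 among all treated patients, and e the corresponding risk in the extension among enrollees.

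- Section 9.2 percentage: e
- Cumulative risk from first parent dose: d + (1 - d)e
- Shortfall: d + (1 - d)e - e = d(1 - e), positive whenever d > 0
- Crude percentage in the synopsis set: (1200d + 800e)/1200

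The cumulative formula applies e to everyone who did not stop for an adverse event in Weeks 0-24, including those who did not roll over for other reasons. The documents give no adverse-event rates, so d and e below are assumptions.

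| d | e | Section 9.2 | Cumulative from first dose | Shortfall (points) | Crude, synopsis set |
|---|---|---|---|---|---|
| 1% | 3% | 3.0% (24/800) | 3.97% | 0.97 | 3.0% (36/1200) |
| 1% | 5% | 5.0% (40/800) | 5.95% | 0.95 | 4.3% (52/1200) |
| 1% | 8% | 8.0% (64/800) | 8.92% | 0.92 | 6.3% (76/1200) |
| 5% | 3% | 3.0% (24/800) | 7.85% | 4.85 | 7.0% (84/1200) |
| 5% | 5% | 5.0% (40/800) | 9.75% | 4.75 | 8.3% (100/1200) |
| 8% | 3% | 3.0% (24/800) | 10.76% | 7.76 | 10.0% (120/1200) |
| 8% | 8% | 8.0% (64/800) | 15.36% | 7.36 | 13.3% (160/1200) |

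Over d = 1% to 8% and e = 3% to 8%, the shortfall runs from about 0.9 to 7.8 points.

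**5. Changing the denominator alone does not cure it.** The crude percentage in the synopsis set simplifies to d + 2e/3, which is below e whenever d < e/3. At d = 1%, e = 3% both sets give 3.0%. At d = 1%, e = 5% the larger set gives 4.3% against 5.0%. Patients who did not roll over add to the denominator but have no extension follow-up.

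**6. Any adverse event in Weeks 0-24.** Suppose 60% of 800 enrollees have an event. If 80% of the other 400 do, the all-treated figure is (480 + 320)/1200 = 66.7%, and the enrollee figure is 6.7 points too low. If only 50% do, it is (480 + 200)/1200 = 56.7%, and the enrollee figure is 3.3 points too high. The direction depends on the non-enrollees.

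**The case against.** The strongest reply is that the safety objective (synopsis and Section 3) is itself conditional: it concerns patients who had already completed 24 weeks in a parent study. The Section 9.2 population answers that question, and the Amendment 3.1 summary of changes shows the move to enrollees was deliberate. On this view the synopsis sentence is an unrevised leftover. This stands as an account of intent, and it is why the enrollee population is a legitimate choice. It does not remove the conflict in the current text, nor does it make a pooled figure on the Section 9.5 clock a risk from first dose.

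Reading study drug in the synopsis sentence as extension drug would reconcile the two. That is strained, since the sentence refers to all parent-study patients and a window from parent Baseline.

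Three further points on the other side hold:

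- Early events are not lost. The Schedule of Activities (footnote aa) has events with onset before the first extension dose reported in the parent study.
- The only safety analysis with a decision rule, lumbar spine bone density against -2.2%, is already limited in the synopsis to Group A patients who enrolled in the extension. It is unaffected.
- The rest of the safety analysis is descriptive, and no table shell is shown that promises a cumulative incidence from parent Baseline.

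A reader might infer that adverse-event rates in general will be biased low, or that discontinuation rates will be shown at about half their true value. The documents do not support either. Step 6 shows that the any-event percentage can err in either direction, and a factor of about one half needs assumed rates such as d = 5% with e = 5%.

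**Conclusion.** The contradiction between the synopsis and Section 9.2 is certain and involves up to about 400 of 1200 planned patients. It is also certain that enrollee-only tables on the Section 9.5 clock show no permanent adverse-event discontinuations in Weeks 0-24 and omit the events behind them. Read as a risk from first parent dose, the discontinuation figure is too low by d(1 - e). The size cannot be derived from the documents; the range in step 4 rests wholly on assumed rates.

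Understatement is established only for adverse-event discontinuations and treatment-limiting events. It does not follow that the safety evaluation as a whole is invalid, that the enrollee population is the wrong choice for the stated objective, or that person-time or Kaplan-Meier analysis of every parent-study patient is obligatory. This should be fixed before the safety tables are produced, because it changes what they can be said to show.

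**What to change.** Align the synopsis safety paragraph, the opening of Section 9, Section 9.2 and Section 9.5 on one Safety Population.

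**If the Section 9.2 enrollee population is kept:**

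- Correct the synopsis sentence to match.
- Present adverse events and adverse-event discontinuations separately for Weeks 0-24 and from the first MVT-601-3103 dose.
- State that Weeks 0-24 and pooled figures are conditional on completing the parent study.
- Do not report a pooled discontinuation percentage as the risk from first parent dose.

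**If a risk from first parent dose is also wanted:** compute it in all treated parent-study patients with exposure-adjusted or time-to-event summaries, because a crude percentage is diluted by patients who did not roll over.

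The cost is protocol and SAP wording and some extra tables. Event collection already separates at the first extension dose, so no new data are needed. Some rates may look less favorable.
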